#### Subgroup analysis

Depending on clinical relevance, exploratory subgroup analyses may be proposed after studying the subgroup × arm interaction in the above-mentioned regression models.

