### 3.3. Study diagram

[figure not shown]
The study assesses the benefits of UVGI devices placed in communal living spaces to reduce the incidence and severity of ARI in Nursing Home residents. In all the Nursing Homes included, UVGI devices will be installed and commissioned at the start of the study. Some UVGI devices will be deactivated by installing an invisible internal filter. The inactivation filters will be installed by a technical team independent of the investigation team. Inactivation will therefore be carried out blind to the study team, care givers and statistician.

Participating Nursing Homes will be randomized into two arms:

- In arm A: UVGI devices will be left active during period 1, and filtered (i.e. deactivated) during period 2.
- In arm B: UVGI devices will be filtered (i.e. deactivated) during period 1 and will remain active during period 2.

The two periods will last 7 months each, and will take place two years in a row on the same dates (October 1 to April 30). They will be separated by a 5-month wash-out period (May 1 to September 30), during which all UVGI devices will be switched off in both arms.

Figure1 . Study diagram

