### 3.4. Randomization

The centers included will be randomized into arms A and B in a 1:1 ratio, using a centralized computerized system.

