### Main analysis

The main comparison will focus on the incidence of first severe ARI between follow-up periods with an unfiltered UV device and follow-up periods with a filtered UV device. The numerator will be the number of people who experienced at least one severe ARI during a period. The denominator will be the cumulative time spent in the nursing home until the first ARI or exit from the period.

The result will be expressed as an incidence ratio with a 95% confidence interval.

In the first instance, the analysis will be carried out at the individual level. A generalized linear mixed model will be used, with a Poisson distribution or a negative binomial distribution in the case of overdispersion, a logarithmic link function and an *offset* term for the number of patient-years. The model will take into account not only intervention and period fixed effects, but also random effects at cluster, cluster-period, cluster-individual and individual levels. The correlation structure will be of the exchangeable block type.

In the second instance, if the model does not converge, we will perform the analysis at the cluster level (Hayes RJ, Moulton LH. *Cluster Randomised Trials*. CRC Press; 2017. <https://books.google.fr/books?id=iklrDwAAQBAJ> p197).

Sensitivity analyses will be carried out:

- Using the cumulative incidence of severe ARI as the endpoint, with the total number of severe ARI in the numerator and the cumulative time spent in the nursing home until exit from the period in the denominator. The model will be the same as the main model, with the addition of a random individual-period effect.
- By adjusting the model on the following variables: gender, age, GIR index. The last two variables will be measured at the start of each period.

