### Analysis of clinical secondary endpoints

- Analyses of clinical secondary endpoints will focus on:
  - Incidence of symptomatic ARIs of all grades
  - Incidence of all-cause hospitalization, all-cause mortality, and all-cause "hospitalization or death"
  - Incidence of non-infectious adverse events of interest, overall and by severity grade (CTCAE classification).
- Analyses of clinical secondary endpoints will focus on the occurrence of the 1st event and will be performed without adjustment. Sensitivity analyses will be performed:
  - Using cumulative incidence as the endpoint
  - By adjusting the model on the following variables: age, gender, GIR index.
- Analyses of clinical secondary endpoints will use the same model as that used for the primary analysis, or equivalent models appropriate to the frequency of events.

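### The subgroup section names a subgroup × arm interaction, but the arms are crossover sequences; the term that measures effect modification is subgroup × intervention

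*Protocol*

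**What the plan says.** Section 7.2 (Subgroup analysis) states that, depending on clinical relevance, "exploratory subgroup analyses may be proposed after studying the subgroup × arm interaction in the above-mentioned regression models". No subgroup, threshold or decision rule is given.

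Section 3.3 defines the arms as two orders of treatment. The first order reads "In arm A: UVGI devices will be left active during period 1, and filtered (i.e. deactivated) during period 2". The second is its mirror image, with the inactive winter coming first: "In arm B: UVGI devices will be filtered (i.e. deactivated) during period 1 and will remain active during period 2". Section 3.4 randomises homes to these arms: "The centers included will be randomized into arms A and B in a 1:1 ratio, using a centralized computerized system". Section 6.1 uses the word in the same sense when it says when filters go in and come out.

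The treatment condition goes by other names. The main analysis compares incidence "between follow-up periods with an unfiltered UV device and follow-up periods with a filtered UV device". Its model is described so: "The model will take into account not only intervention and period fixed effects, but also random effects at cluster, cluster-period, cluster-individual and individual levels". For the clinical secondary endpoints, "Analyses of clinical secondary endpoints will use the same model as that used for the primary analysis", or an equivalent suited to how frequent the events are. None of these descriptions contains an arm or sequence term.

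**The concern.** An interaction test for a subgroup analysis should ask whether the effect of active versus inactive UVGI differs between, say, more and less dependent residents. In a parallel-group trial arm and treatment are the same thing, so subgroup × arm asks that question. In this two-period crossover they are not. Every home contributes one active and one inactive winter, and arm records only the order. A subgroup × arm term therefore compares the two orders of treatment, each summed over both conditions.

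An analyst who added a sequence term and interpreted its interaction would have a statistic with almost no relation to effect modification. A null result would be no reassurance that the effect is homogeneous, and a positive result would be no evidence that it varies.

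**Working it through.** The protocol gives no figure on this point to reproduce. The check is which contrast each term estimates, and then how large the matter is at the trial's size.

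**Step 1: what subgroup × arm estimates.** In subgroup *s*, let the inactive-device rate be λ in winter 1 and kλ in winter 2, and let active UVGI multiply it by r. With equal person-time, expected events summed over both winters are proportional to:

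- Arm A (active, then inactive): λ(r + k)
- Arm B (inactive, then active): λ(1 + k·r)

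The A-to-B ratio within the subgroup is R = (r + k)/(1 + k·r). The subgroup × arm ratio is R in one subgroup divided by R in the other. If k = 1, then R = (r + 1)/(1 + r) = 1 for every r, so the interaction ratio is exactly 1.00.

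The same holds on the log scale with the two winters weighted equally. Each arm averages (log r + log k)/2 above the winter-1 inactive log rate, so the arms do not differ in any subgroup. The small departures below arise because a Poisson fit weights the winters by their event counts.

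**Step 2: numbers.** The subgroup rate ratios and the values of k are illustrative assumptions, not protocol figures. The true ratio is the second rate ratio divided by the first.

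| Rate ratios by subgroup | k | R in each subgroup | Subgroup × arm | True ratio |
|---|---|---|---|---|
| 0.25 and 1.00 | 1 | 1.00; 1.00 | 1.00 | 4.0 |
| 0.25 and 1.00 | 1.5 | 1.75/1.375 = 1.27; 1.00 | 1.27 | 4.0 |
| 0.25 and 1.00 | 0.67 | 0.92/1.1675 = 0.79; 1.00 | 0.79 | 4.0 |
| 0.35 and 0.70 | 1.5 | 1.85/1.525 = 1.213; 2.20/2.05 = 1.073 | 1.13 | 2.0 |
| 0.35 and 0.70 | 2 | 2.35/1.70 = 1.382; 2.70/2.40 = 1.125 | 1.23 | 2.0 |

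A Poisson log-linear model fitted to exact expected counts gave the same subgroup × arm values. With subgroup × intervention it returned 2.0 and 4.0 in every row, whatever the value of k.

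**Step 3: rejection rates.** 400 trials per scenario were simulated and tested at two-sided 0.05. Assumptions: two equal subgroups, a baseline rate ratio of 1.5 between them, and cluster and cluster-period standard deviations of 0.2 on the log scale. The analysis was a Poisson model with fixed cluster effects.

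| Rate ratios; k | Subgroup × arm | Subgroup × intervention |
|---|---|---|
| 0.50 and 0.50; 1 (no modification) | 5.5% | 4.25% |
| 0.25 and 1.00; 1 | 6.75% | 99.25% |
| 0.25 and 1.00; 1.5 | 17.75% | 100% |

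The Monte Carlo standard error near 5% is √(0.05 × 0.95/400) ≈ 1.1 percentage points, so 6.75% is not distinguishable from the nominal level.

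**Step 4: what the correct test could deliver for a less extreme difference.** Section 7.1 gives 12 homes, about 90 residents each, and an ARI incidence of 17 per 100 patient-years without UVGI; each period lasts 7 months.

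- Inactive person-time: 12 × 90 × 7/12 = 630 patient-years
- Inactive-period events: 630 × 0.17 = 107.1, or 53.6 in each of two equal subgroups
- Active-period events for rate ratios of 0.5 and 1.0: 26.8 and 53.6
- SE of the log ratio of rate ratios, ignoring clustering: √(3/53.6 + 1/26.8) = √0.0933 ≈ 0.31
- Expected |z| = ln 2/0.3055 = 0.693/0.3055 ≈ 2.3
- Power ≈ Φ(2.27 − 1.96) = Φ(0.31) ≈ 0.62

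**The case against.** The best defence is that *arm* is loose wording carried over from parallel-group trials. The interaction is to be studied in models already described, and the only treatment variable in them is intervention; the main model itself would need a sequence term added before the literal reading could be fitted. Many statisticians would read the sentence as intended. That is plausible, and it is a reason to rate the point low. But the protocol gives *arm* one meaning throughout, and I found no place where it means active versus inactive. The two coincide only within a single period, as in the parallel comparison the DSMB may request after period 1, and the models in question span both periods.

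A second defence is that the analysis plan will fix the term. Section 7.2, however, presents this text as the principles that guide that plan. The point concerns a term that the protocol names, not a detail left for later.

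Three stronger readings are tempting, and the documents do not support them:

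- *That subgroups pass or fail on a meaningless test.* The section says only that analyses may be proposed after the interaction is studied. It sets no threshold and no pass/fail rule.
- *That the literal term can never respond to effect modification.* That is exact only for equal winters. Otherwise a small trace remains, with a direction set by which winter was worse. It is still not a valid test.
- *That the wording costs the trial a decisive test.* For rate ratios of 0.5 versus 1.0 the correct interaction has an expected |z| of about 2.3, so real differences could be missed with it too.

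**Conclusion.** The point stands as a named analysis term that, on the protocol's own definitions, does not measure what a subgroup analysis needs. Nothing else in the design depends on it: the primary and secondary comparisons, the sample size and safety monitoring are unaffected. With the optional, exploratory status of these analyses, that makes the importance low.

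The result for equal winters is algebraic and needs no assumption about the size of the effects. The figures for unequal winters rest on the assumed rate ratios, equal person-time and the assumed ratio of winter incidences. The power figure of about 60% rests on section 7.1's incidence, which is stated for ARIs without restriction to severe ones, on two equal subgroups and on no clustering. It indicates scale and is not a design calculation.

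**What to change.** In section 7.2 (Subgroup analysis), replace the subgroup × arm interaction with the subgroup × intervention interaction, adding in brackets that this means active versus inactive UVGI. State that the period fixed effect and the random effects of the main model are kept. The analysis plan should use the same wording; it could also include a subgroup × period term, so that a difference between subgroups in how the two winters compare is not confused with effect modification. In the exact-count check, adding that term left the estimates at 2.0 and 4.0.

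The cost is a wording correction, with no consequence for data collection, design, sample size or blinding.

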#### Missing data

For explanatory variables missing in less than 10% of participants, and verifying the hypothesis of the random nature of this loss of information, multiple imputation may be proposed. For explanatory variables missing in more than 10% of residents, no imputation will be performed and these covariates will not be included in multivariate analyses.

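### The 10% completeness rule could remove GIR for every resident from the pre-specified adjusted sensitivity analyses, where multiple imputation would keep it

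*Protocol*

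**What the plan says.** The Missing data paragraph of protocol section 7.2 splits covariates at a 10% threshold. The lower branch begins "For explanatory variables missing in less than 10% of participants" and allows multiple imputation as an option, provided the loss can be regarded as random. The upper branch, for covariates missing in more than a tenth of residents, is categorical: "no imputation will be performed and these covariates will not be included in multivariate analyses".

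The covariates to which this applies are named in the same section. The Main analysis paragraph lists a sensitivity analysis "By adjusting the model on the following variables: gender, age, GIR index" and adds, of age and GIR, that "The last two variables will be measured at the start of each period". The paragraph on clinical secondary endpoints has a matching sensitivity analysis: "By adjusting the model on the following variables: age, gender, GIR index". No sentence exempts these three from the 10% rule.

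The main analyses do not use them. The primary model has "intervention and period fixed effects" plus random effects, and the analyses of clinical secondary endpoints "will focus on the occurrence of the 1 st event and will be performed without adjustment".

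**The concern.** The rule works the wrong way round. When little is missing and the choice of method hardly matters, imputation is allowed. When more is missing and a principled method would help, imputation is forbidden and the covariate goes. Removal applies to the variable and not to the incomplete records, so every observed value is lost with it.

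GIR is the realistic casualty. Age follows from month and year of birth and gender is basic record data (section 6.5.1). GIR is a clinical score that has to be current at the start of each period. It is also the only dependency measure of the three.

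What is at stake is the content of the pre-specified check on case-mix. The trial has 12 clusters and an open cohort with turnover between periods. If GIR is dropped, the analysis presented as adjusted for age, gender and dependency adjusts for age and gender only.

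**Working it through.** The plan states no figure to reproduce here. The check sets the passages side by side and puts the threshold on the scale of the trial.

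**Inputs (section 7.1):** 12 homes, about 90 residents per home, 80% of residents present in both periods, constant home size.

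**Scale of the threshold**
- Residents per period: 12 × 90 = 1,080.
- Distinct residents over two periods: 1,080 + 0.20 × 1,080 = 1,296.
- Resident-period records: 2 × 1,080 = 2,160.
- 10% of each: 108, about 130, and 216.

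The rule does not say which of these counts applies. It speaks of participants in one branch and residents in the other, and leaves exactly 10% uncovered.

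**What crossing the threshold does, for one period**
- At 9% missing: 0.09 × 1,080 ≈ 97 scores missing. GIR stays and imputation is optional. If it is not used, a complete-case adjusted model leaves those residents out.
- At 11% missing: 0.11 × 1,080 ≈ 119 scores missing. GIR is removed for all, so 1,080 − 119 = 961 recorded scores go unused.

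Twenty-two more missing scores (119 − 97) change the model for 1,080 residents.

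**Could the threshold be crossed?** Four places bear on this.
- Section 7.2, Main analysis: GIR is needed at the start of each period.
- Section 6.5.1: GIR is in the baseline list and absent from the follow-up list.
- Table 1 (section 6.3): baseline collection for residents already present is marked at T0 only; for new residents, at T1, T2 and T3.
- Time T3 in section 6.2: clinical data are collected as in T1, without saying whether baseline items are taken again.

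These do not settle whether continuing residents get a second GIR score. The two ends of the range, as assumptions:
- *GIR re-scored and captured for all:* missingness could be near 0% and the rule never applies.
- *GIR recorded only once, at entry, and the old score not accepted as the period-2 value:* missing records = 0.80 × 1,080 = 864. That is 864/1,080 = 80% of period 2, or 864/2,160 = 40% of all resident-period records. GIR is removed on either count. The recorded scores thrown away would be 2,160 − 864 = 1,296, and each of the 864 residents affected has an earlier score from which to impute.

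**The case against.** The strongest reply is that no main result is touched, and this stands. Age, gender and GIR enter only sensitivity models. A reader might infer that the rule biases the primary rate ratio or weakens the primary test. The documents do not support that, because the primary model contains none of these covariates.

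Second, the trigger is hypothetical. Baseline data come from nursing home records, research assistants have online access to the care records (section 6.2), and section 7.2 says GIR will be measured at the start of each period. This stands in part. A reader might infer that GIR will be lost. The documents give no expected missingness, and the 40% case assumes that the second measurement is not made. But the collection list and Table 1 do not provide for that measurement for continuing residents, so the risk is not fanciful.

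Third, the cut-off is fixed in advance, does not look at outcomes, and is applied by blinded staff, so it opens no route to choosing a model by its result. That is correct. The objection here is to a poor rule and not to data-driven selection.

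Fourth, section 7.2 only guides a separate analysis plan, which may refine it. That is possible, but the text is categorical, and a plan that follows the protocol inherits the rule.

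Three further readings should be resisted.
- Describing GIR as the main prognostic covariate goes beyond the documents, which do not rank the three. Any gain in precision from GIR is also unquantified, and each home acting as its own control, with the cluster and individual random effects, may already absorb part of the stable case-mix.
- Faulting the plan for claiming to prove that data are missing at random leans too hard on one phrase, which can be read as requiring the assumption to be reasonable.
- A missing-indicator method might be thought safe because the comparison is randomised. Period-2 GIR is recorded after randomisation and after period-1 exposure, so that argument does not carry over.

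**Conclusion.** The concern holds in a limited form. As written, the rule can strip GIR from the adjusted sensitivity analyses of the primary and clinical secondary endpoints. It would do so for every resident, at a threshold of about 108 missing scores per period, 130 residents or 216 resident-period records, depending on the count used. These counts rest on the planned 12 × 90 residents with 80% overlap.

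The effect on the adjusted rate ratio or its standard error cannot be derived from the documents. Whether the rule is triggered depends on GIR completeness, above all on re-recording at the start of period 2, for which anything from near 0% to 40% of records missing is compatible with the text. This is a worthwhile improvement at low cost and no threat to the trial's main conclusion.

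**What to change.** - Delete the 10% exclusion rule for the pre-specified covariates. Keep age, gender and GIR in the adjusted models whatever their completeness.
- Pre-specify multiple imputation of missing values as the method, no longer as an option. The imputation model should respect the cluster and period structure and use a resident's earlier GIR value where there is one. Add a complete-case analysis as a check.
- State whether GIR is recorded again at the start of period 2 for continuing residents, and bring section 6.5.1 and Table 1 into line with section 7.2. If it is not, state how the earlier score is used.

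The cost is wording and a little more analysis work. The change can be made in the analysis plan, which section 7.2 says will be validated and made public before analysis begins, with the departure from the protocol rule declared there. If the protocol text itself is amended, section 13.2 requires a new ethics committee review.

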#### Intermediate analysis

No interim analysis is planned for this study. The Data and Safety Monitoring Board may request a parallel exploratory analysis (group A vs. group B) after the end of the 1st period if it wishes to explore the hypothesis of premature evidence of efficacy or futility. If an analysis is performed for efficacy, the Haybittle-Peto stopping rule will be used: p-value=0.0027. This rule being conservative, the significance level would remain at  $\alpha=5\%$  for the final analysis.

#### Other points to watch

The DSMB will be vigilant for the emergence of signs suggestive of toxicity, even if the evidence currently available strongly suggests that the risk of toxicity is very low.

The DSMB will pay particular attention to the appropriateness of the choice of the primary endpoint. When the study was designed, the investigators hesitated between choosing a broad primary endpoint including all high and low ARIs, whatever their severity, and a more restrictive primary endpoint including only severe low ARIs. Uncertainty was linked in particular to the absence of reliable recent data allowing to estimate the impact of either of these two options on the trial conduct. The DSMB will assess the relevance of the chosen primary endpoint in the light of the incidence observed, and may, if it so wishes, recommend a change in the definition of this endpoint, provided that the arguments presented for this change do not call into question the principle of quadruple blinding.

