#### *9.1.3. Role*

The Scientific Advisory Board's mission is to ensure that the research is carried out appropriately, from a scientific, ethical and logistical point of view.

- It ensures that the research runs smoothly and that the protocol is respected,
- It ensures that all investigators and other research participants are kept informed,
- It ensures the scientific follow-up of the research: maintaining the relevance of the research questions and the validity of the methods used to answer them,
- It oversees the application of rules governing access to research data and the communication and publication of research results,
- It maintains a permanent link with the sponsor and the DSMB,
- It decides on any relevant modifications to the protocol necessary for the continuation of the research, in particular:
  - Amendments to the protocol,
  - Decisions to open or close study sites.

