### 9.2.3. *Role*

The DSMB has an advisory role for the sponsor, the coordinating investigator and the Scientific Advisory Board. It gives a general opinion on the progress of the trial. It can help to make difficult decisions during the course of the trial, for which an independent judgment is desirable. In particular, it advises on :

- Premature termination of the trial (due to toxicity or futility, because the trial is no longer feasible, or because the elements needed to reach a conclusion have already been gathered);
- Extensive modifications to the protocol that may become necessary to take account new scientific data;
- Interpretation of analysis results or need for intermediate analysis.

The opinion of the DSMB is sent in writing to the Coordinating Investigator, the Sponsor, and the Chairperson of the Scientific Advisory Board.

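### Section 7.2 lets the DSMB recommend a new primary endpoint from the observed incidence, without requiring pooled incidence or that no A-versus-B comparison has been seen

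*Protocol*

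**What the plan says.** Two neighbouring parts of Protocol Section 7.2 matter.

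- **Other points to watch.** The investigators hesitated between a broad endpoint (all upper and lower ARIs of any severity) and a narrow one (severe lower ARIs only). The reason given is lack of data: "Uncertainty was linked in particular to the absence of reliable recent data allowing to estimate the impact of either of these two options" on the conduct of the trial. Hence the review: "The DSMB will assess the relevance of the chosen primary endpoint in the light of the incidence observed". The board may recommend a change of definition, "provided that the arguments presented for this change do not call into question the principle of quadruple blinding".
- **Intermediate analysis.** No interim analysis is planned, but the DSMB "may request a parallel exploratory analysis (group A vs. group B) after the end of the" first period, if it wishes to explore premature evidence of efficacy or futility. A Haybittle-Peto threshold of p = 0.0027 applies if the look is for efficacy.

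The governance sections add the following. The DSMB advises, and its remit includes "Interpretation of analysis results or need for intermediate analysis" (Section 9.2.3). On reporting: "The opinion of the DSMB is sent in writing to the Coordinating Investigator, the Sponsor, and the Chairperson of the Scientific Advisory Board". The Scientific Advisory Board decides on amendments, and "It maintains a permanent link with the sponsor and the DSMB" (Section 9.1.3). Every amendment returns to the ethics committee (Section 13.2). Section 3.3 lists the study team, care givers and statistician as blind to filter status; it does not name the DSMB.

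**The concern.** Whether an endpoint yields enough events is answered by incidence pooled over both groups. A choice made that way is approximately independent of the treatment contrast and leaves the final test at its nominal level. A choice made after seeing A versus B is different. In period 1, arm A is active and arm B is filtered, so that comparison is the treatment comparison, and the same data are used again in the final crossover test. If the endpoint is redefined by someone who knows which definition separates the groups better, a chance difference in period 1 can be carried into the final result.

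Section 7.2 gives both powers to one board and sets no order between them. Its single condition governs what is argued, not what has been seen. A board could see the contrast and then give a frequency argument that respects blinding in form. Masking the letters A and B would not prevent this, since picking the larger absolute contrast needs no label.

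**Working it through.** **Does any text close the gap?**

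| Provision | Requires pooled incidence? | Bars a recommendation after an A-versus-B look? |
|---|---|---|
| 7.2, endpoint review | No | No |
| 7.2, blinding proviso | No; limits the arguments | No |
| 7.2, purpose of the A-versus-B look (efficacy or futility) | No | No |
| 7.2, p = 0.0027 rule | No; governs stopping for efficacy | No |
| 3.3, list of blinded parties | No; DSMB not listed | No |
| 9.1.3, Scientific Advisory Board decides | No | No |
| 9.2.3, written DSMB opinion | No | No |
| 13.2, ethics committee review | No | No |

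**The plan's own figure.** The only error figure attached to the look is 0.0027. It reproduces: 2 × (1 − Φ(3.00)) = 0.0027. It says nothing about endpoint choice.

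**Illustrative size.**

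1. Inputs from Section 7.1: m = 90 residents per home, within-period ICC ρ = 0.1, individual autocorrelation 0.2, 80% of residents present in both periods. For the between-period ICC η, Section 7.1 gives 0.05 (cluster autocorrelation 0.5) and also calls it negligible. Both 0.05 and 0 are used.
2. Correlation of a home's two period means: r = [mη + 0.8 × 0.2 × (1 − ρ)] / [1 + (m − 1)ρ].
   - η = 0.05: r = (4.5 + 0.144) / 9.9 = 4.644 / 9.9 = 0.469.
   - η = 0: r = 0.144 / 9.9 = 0.0145.
3. The period-1 statistic compares homes on Y1. The final statistic compares them on Y1 − Y2. With equal variances their correlation is (1 − r) / √[2(1 − r)] = √[(1 − r)/2].
   - η = 0.05: √(0.531/2) = 0.515.
   - η = 0: √(0.9855/2) = 0.702.
4. Assumptions not in the protocol: the statistics of two candidate endpoints correlate at 0.3 to 0.9 under the null, and the endpoint with the larger absolute period-1 contrast is always kept. That endpoint is then tested on all data at two-sided 0.05 (normal approximation, simulated null trials).

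| Endpoint correlation | Error, η = 0.05 | Error, η = 0 |
|---|---|---|
| 0.3 | 6.7% | 8.0% |
| 0.5 | 6.6% | 7.7% |
| 0.7 | 6.3% | 7.2% |
| 0.9 | 5.8% | 6.3% |

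With the endpoint fixed, or chosen without regard to the contrast, the same simulation gives 5.0%.

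**The case against.** The strongest reply is that the text already points the right way. The A-versus-B look is allowed only to explore premature efficacy or futility, so it is tied to stopping and not to endpoint choice. The endpoint review has its own reason, the effect on trial conduct, which is a matter of event counts. The proviso excludes an argument built on the arm difference. Harm would need a chain: an optional look is taken, it influences the board, the board argues from frequency, and the Scientific Advisory Board and ethics committee accept. The order in which a DSMB sees its tables is also often set outside a protocol.

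Most of this stands, and it makes the point a modest one. It does not remove it, because the protocol itself grants the power and writes its one condition, and that condition is aimed at the argument and not at knowledge of the contrast.

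Three stronger readings are tempting and should not be made.

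- **That an endpoint was changed after a comparative look.** Protocol Versioning dates version 3 to 23/09/2025, after period 1 ended on April 30, 2025, and attributes its edits to DSMB recommendations. It does not say what was edited or what the board had seen.
- **That 5.8% to 8.0% is this plan's error rate.** It belongs to an assumed misuse rule that the protocol neither states nor suggests.
- **That the final 5% level is misstated.** The sentence "This rule being conservative, the significance level would remain at" 5% describes the level of the final test. It does not claim that overall error is exactly 5% if the optional look is taken.

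**Conclusion.** The point holds as a permissive rule, not as evidence of misuse. Section 7.2 neither confines the endpoint review to incidence pooled over A and B nor separates it from a possible A-versus-B look, and no governance section does so. This conclusion rests on the text alone and needs no calculation.

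The size cannot be derived from the protocol, which gives no selection rule and no correlation between candidate endpoints. The illustrative range shows that the route is not trivial if used in the worst way. With pooled incidence it is closed. Correcting this is a cheap improvement, not a condition for the validity of the design.

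**What to change.** 1. In Section 7.2, Other points to watch, state that any DSMB recommendation on the primary endpoint rests only on incidence pooled over A and B, and is made before any A-versus-B comparison has been seen, or by members who have not seen one.
2. In Section 9.2.3, require the DSMB's written opinion on the endpoint to record whether A-versus-B data had been seen. Apply this also to any endpoint recommendation already made after period 1.

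The cost is one or two sentences in Section 7.2 and one in Section 9.2.3. The downside is that, once a comparative look has been taken, an endpoint change can be recommended only by members who have not seen it, even if the incidence then proves unsuitable; with a three-member board (Section 9.2.1) this may leave few or none. Pooled incidence fully serves the purpose that the protocol gives for the review, so nothing needed for that purpose is lost.
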